#### **-80°C Freezer**

A dedicated -80°C freezer located at the Heintz laboratory will be available for storage of study samples, including nasopharyngeal, conjunctival, buccal, and rectal swabs.

### **7.2.6 Protocol for Tubing and Handling of Samples**

The tubing and handling protocol must be carefully followed in order to prevent contamination and ensure the safe transport of the samples back to the Heintz

laboratory and/or to other institutions for processing. The person in charge of labeling, tubing, arranging, and handling the samples needs to perform this task in the most orderly and attentive manner.

1. Both hands of the tuber should be gloved at all times. The tuber's gloves only need to be changed when any potential contamination of the gloves occurs. The tuber opens the capped, hinged lid of a microcentrifuge tube, which has been labeled with the participant's random identification number.
2. The investigator/study coordinator should screw the cap of the microcentrifuge tube tightly, flick the tube to mix the sample with the media (for tubes with DNA/RNA shield media), and place it in the sample collection box until transfer to a -80C for storage in the Heintz lab.

All samples will be in sample boxes, labeled with the participant's study number for easy future identification.

## **Chapter 8: Training**

### **8.1 Standardization**

The research team will work together prior to the baseline visit to standardize all study procedures. We will review the format, general logistics, and procedures for all participants. Training and standardization of sample processing will be under the guidance of [name].

## **Chapter 9: Sample Organization, Transport, and Storage**

### **9.1 De-identification**

All specimens will be labeled in the outpatient clinic with a random identification number linked to their name, MR number, and surgical/ocular disease history, but to facilitate masking, only the designated Study Coordinator and the Biostatistician will have access to the key linking the ID with patient information. Age, gender, and surgical/ocular disease history will be available for each specimen, but names will be kept confidential. Therefore, all specimens will be de-identified. Please note that the Study Coordinator who is unmasked to the study arms will not be collecting samples at 1-week post-op (primary end point) to prevent potential biases.

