## **Chapter 3: Study Design**

The research team will assess antibiotic resistance over four weeks, comparing frequency of antibiotic use among adult patients undergoing ocular surgeries. All eligible participants will be randomized. A random sample of 108 (36/arm) participants from UCSF will be selected to participate in the "ARIES" study, which will entail biospecimen collection via nasopharyngeal, conjunctival, buccal, and rectal swabs 1-week post-op. Baseline will entail conjunctival swab collection. 4-week post-op sample collection will include conjunctival, nasopharyngeal, and buccal swabs. All biologic specimens collected will be stored and made available to [name] for laboratory testing of antibiotic resistance.

[figure not shown]

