### **3.1. Randomization**

**Randomization of Treatment Allocation.** All eligible UCSF adult patients undergoing ocular surgery will be randomized in a 1:1:1 fashion to three groups:

- **Group 1:** intraoperative/intracameral antibiotic (moxifloxacin) only; no postoperative antibiotic drops
- **Group 2:** intraoperative/intracameral antibiotic (moxifloxacin); postoperative antibiotic drops four times a day for 1 week and then stop
- **Group 3:** intraoperative/intracameral antibiotic (moxifloxacin); postoperative antibiotic drops once a day for 1 week and then stop

Refer to SAP for randomization details.

**Study Participants:** UCSF adult patients undergoing ocular surgeries will be recruited if they consent and the study doctor deems the participant meets all study criteria.

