#### 4.2. Study Schedule

The schedule for examination and treatment is shown below in Table 1:

	Pre-Op	1-Day Post-Op	1-Week Post-Op	4-Week Post-Op
Consent	X			
Randomization	X			
Specimen Collection	X		X	X
Survey		X	X	X

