### **Enrollment**

The study will be explained by the study doctors or study coordinators. The patient will be enrolled in the study after obtaining written consent from the patient (and witness if needed).

The participant will be randomly assigned to one of three groups only after obtaining consent.

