### **Specimen Collection**

All participants will have NP swabs, conjunctival swabs, and buccal swabs collected by the study doctors or study coordinator. Rectal swabs will be collected by the patient themselves by following instruction guide (see Appendix).

All specimens will immediately be placed in a Zymo preservative after collection and labeled with the participants study number. Samples will then be transported to the Heintz laboratory at [name] for long-term storage at -80C and processing.

Conjunctival swabs will be collected prior to surgery. Conjunctival, NP, buccal, and rectal swabs will be collected 1-Week post-op. Conjunctival, NP, and buccal swabs will be collected 4-Week post-op.

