## **Chapter 7: Specimen Collection for Resistance and Microbiome Testing**

### **7.1 Participants**

We will collect nasopharyngeal, conjunctival, buccal, and rectal swab samples from all 108 participants. The swabbing will occur prior to surgery (conjunctival), 1-week post-op (conjunctival, NP, buccal, rectal), and 4-Week post-op (conjunctival, NP, buccal). The enrolled participants will be given instructions on when and where to go for swabbing visits after surgery.

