## **Chapter 9: Sample Organization, Transport, and Storage**

### **9.1 De-identification**

All specimens will be labeled in the outpatient clinic with a random identification number linked to their name, MR number, and surgical/ocular disease history, but to facilitate masking, only the designated Study Coordinator and the Biostatistician will have access to the key linking the ID with patient information. Age, gender, and surgical/ocular disease history will be available for each specimen, but names will be kept confidential. Therefore, all specimens will be de-identified. Please note that the Study Coordinator who is unmasked to the study arms will not be collecting samples at 1-week post-op (primary endpoint) to prevent potential biases.

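### Section 9.1 keeps the unmasked Study Coordinator away from swab collection at 1 week only; extending this to the 4-week swabs is a minor, cheap improvement

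*Protocol*

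**What the plan says.** Section 9.1 (De-identification) acknowledges that one Study Coordinator knows the treatment arms and limits what that person may do. In the Protocol, this coordinator "who is unmasked to the study arms will not be collecting samples at 1-week post-op (primary end point) to prevent potential biases". In the combined document, the coordinator "will not be collecting samples at 1-week post-op (primary endpoint) to prevent potential biases". Both versions name the 1-week visit and no other.

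Chapter 5 (Specimen Collection) sets out who may take the swabs: "All participants will have NP swabs, conjunctival swabs, and buccal swabs collected by the study doctors or study coordinator". It does not vary this by visit. The same paragraph and Section 7.1 give the schedule:

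- before surgery: conjunctival;
- 1 week: conjunctival, nasopharyngeal, buccal and rectal;
- 4 weeks: conjunctival, nasopharyngeal and buccal.

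The rectal swab is self-collected and is taken only at 1 week, so every 4-week swab is taken by staff.

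Three other statements bear on the point. Chapter 3 gives the horizon: "The research team will assess antibiotic resistance over four weeks". Section 3.1 limits the drops to the first week, for example in Group 3: "postoperative antibiotic drops once a day for 1 week and then stop". Chapter 6 masks laboratory personnel by using a random identification number.

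**The concern.** The plan itself accepts that a collector who knows the arm could bias a sample, and it acts on that at 1 week. Nothing in its reasoning is peculiar to 1 week, except that 1 week is the primary end point. The same three staff-collected swab types are taken by the same procedures at 4 weeks, where the written rule is silent. Staff who follow Section 9.1 literally could let a person known to be unmasked collect at an outcome visit after randomization.

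What is at stake is the 4-week comparison between arms. It is the only collection scheduled after the 1-week visit, when the drops end, so it is the only look at resistance some time after exposure. The nasopharyngeal and buccal swabs have no pre-operative sample, so their 4-week comparison cannot be set against a baseline value. That makes even-handed collection somewhat more useful there.

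**Working it through.** No power, alpha or sample-size formula applies, and the plan states no figure to reproduce. The check sets the provisions side by side and counts visits.

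**Coverage of the rule by visit** (Table 1 in Section 4.2; Section 7.1; Section 9.1)

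| Visit | Staff-collected swabs | Unmasked coordinator barred? |
|---|---|---|
| Pre-op | conjunctival | not stated |
| 1 week | conjunctival, nasopharyngeal, buccal | yes |
| 4 weeks | conjunctival, nasopharyngeal, buccal | not stated |

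**Scope count**

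- Collection visits: 3, of which 2 are post-operative. The bar covers 1 of these 2.
- With the 108 planned participants and no dropout, there are 108 × 2 = 216 post-operative collection visits. The bar covers 108 × 1 = 108 of them now and would cover 216 if extended.
- Interval from the 1-week visit to the 4-week visit: 4 − 1 = 3 weeks.

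These counts describe how far the rule reaches. They do not measure bias.

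The pre-op swab is left out of the point. It precedes any study treatment, and the documents do not say whether it is taken before or after randomization.

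**Does the plan's reason carry over to 4 weeks?**

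1. Collection is scripted in Sections 7.2.1 to 7.2.3, but it still depends on the operator: how the fornix is swept, how many of the three permitted nasopharyngeal attempts are made, and how firmly and for how long the cheek is rubbed. These steps are the same at both post-operative visits.
2. Laboratory masking acts after collection. It protects processing but cannot correct a difference in how material was obtained.
3. So the reason given in Section 9.1 applies at 4 weeks as well, with less weight because 4 weeks is not the primary end point.

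**Is there someone else to collect?** The existing bar means that someone other than the unmasked coordinator must already collect at 1 week. Chapter 5 permits study doctors, and the Enrollment paragraph refers to coordinators in the plural: "The study will be explained by the study doctors or study coordinators". The documents do not name the 1-week collector or state the masking status of the doctors or any other coordinator.

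**The case against.** The strongest reply is that nothing here is wrong. Section 9.1 ties its safeguard to the primary end point, which is where a small trial would put it first. The 4-week visit is secondary, and none of the three objectives in Section 1.2 names persistence. The outcome is sequencing and/or directed PCR, the laboratory is masked, the swab steps are scripted, and Section 8.1 provides for standardization beforehand. The bar may also be unnecessary in practice, because another coordinator or a doctor may already collect at 4 weeks. Finally, barring one person does not guarantee a masked collector, because the doctors may also know the arm.

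Most of this stands. It makes the point minor, and it means the edit should ask for a collector who does not know the arm rather than only exclude one person. It does not remove the point: the written rule stops at one visit, its reason does not, and laboratory masking comes too late to help.

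Two stronger readings are tempting, and the documents support neither.

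- A reader might infer that the unmasked coordinator will take the 4-week swabs. The text permits this but does not say so.
- A reader might infer that the 4-week results are biased, or that the plan contradicts its description of the trial as masked. No passage conflicts with another, no size of bias can be derived, and the SAP, listed as Appendix 1 but not in the text reviewed, may define masking roles.

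**Conclusion.** The point holds as a minor improvement to a design choice. The bar on the unmasked coordinator covers 1 of the 2 post-operative collection visits, and the plan's own reason for it applies to the other. The size of any bias cannot be estimated from the documents. It is likely small, and it is zero from this source if someone other than the unmasked coordinator already collects at 4 weeks.

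The conclusion assumes that the SAP does not already extend the bar. Calling the change cheap is an inference: the documents give no staffing figures, and it is assumed that the 1-week collector can also attend at 4 weeks.

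**What to change.** In the current version of Section 9.1, add the words 'or 4-week post-op' directly after the parenthesis that labels 1 week as the primary endpoint. The two documents differ in their eligibility criteria and may be successive versions, so only the one in force needs the edit.

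Have the 4-week swabs taken under the same collector arrangement as at 1 week, choosing a collector who does not know the study arm where one is available. Check the SAP for masking roles first. If it, or existing practice, already covers 4 weeks, say so in Section 9.1.

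The cost is one phrase and less scheduling flexibility at the 4-week visit. Sample size, power, alpha and treatment are unaffected.

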### **9.2 Specimen Transport**

After sample collection, samples from the clinic will be transported to the Heintz laboratory for storage and processing.

### **9.3 Specimen Storage**

Sample storage will occur in two stages: short-term and long-term.

#### **9.3.1 Short-term Sample Storage**

Samples will be labeled with study ID only and are unidentifiable without access to the study database. All samples will be transported to the Heintz laboratory for storage and processing.

#### **9.3.2 Long-term Sample Storage**

All samples processed by the Heintz laboratory will be stored in the -80°C freezer for at least 5 years.

### **9.4 Catalog Specimens**

We will create a list of study data and specimens, including the age, gender, surgical history, ocular disease history, group participant was in, and symptom questionnaire. We will also list the date of collection and transport, and the storage conditions while in the field and while banked at UCSF. This will facilitate identification of specimens for future analyses.

## **Chapter 10: Study Medication**

All adult participants over 18 years of age will be given moxifloxacin intracamerally during surgery. Depending on which group the participant is assigned to, the participants may also be instructed to take topical moxifloxacin at home.

We will monitor as described in the adverse events section. The treatment and monitoring schedule for all study arms is shown in Table 1.

### **10.1 Study Medication Description**

#### **Moxifloxacin**

Will be purchased by the subjects

### **10.2 Dosage Information**

Moxifloxacin will be administered intracamerally during surgery for all participants. The study doctor will use a different moxifloxacin vial for each participant.

All participants in Group 2 and Group 3 will also be taking topical moxifloxacin eyedrops at home.

- Group 2: 4 times a day

- Group 3: once a day

Individuals who are allergic to fluoroquinolones will not be in the study.

### **10.3 Medication Procurement/Donation**

None.

### **10.4 Medication Quality Control**

Intracameral moxifloxacin will be obtained through UCSF pharmacy in compliance with UCSF policy. Topical antibiotics will be dispensed as prescribed. All topical medications are FDA approved.

### **10.5 Adverse Reactions/Side Effects**

Moxifloxacin is generally well-tolerated. The most common side effects of moxifloxacin are diarrhea, nausea, dizziness, and headache, each of which may occur as likely as 4% when taking orally and 8% when taking intravenously. Rarer side effects include dysphagia and stomatitis. Diarrhea due to *Clostridium difficile* has been reported in rare cases.

During the consent process, the common adverse reactions that may occur will be explained to the participant and they will be advised to communicate adverse events to UCSF study staff immediately. If, for any reason, the participant needs further care, they will be referred to the nearest health center for examination and treatment.

The trial sites will be masked to molecular outcomes. There will be no interim analysis given that this is a small study. Statistical monitoring is discussed in the Statistical Analysis Plan. The Data Safety and Monitoring Committee (DSMC) will be given authority to discontinue treatments at any time if there is evidence of unexpected harm.

### **10.6 Adverse Events Systems**

Both active and passive monitoring systems for adverse events are in place for this study. We will monitor adverse events at 1-Day post-op, 1-Week post-op, and 4-Week post-op.

#### **10.6.1 Passive Adverse Events Monitoring**

We will implement a passive monitoring system during the study, by instructing patients to report any adverse events during the study period. Patients will be referred for follow up care on a case-by-case basis.

#### **10.6.2 Active Adverse Events Monitoring**

### **Ocular Symptoms/Quality Survey**

To identify any adverse events during the study, the research team will administer the survey (DEQ-5 and SPEED questionnaires) to each participant at 1-day, 1-week, and 4-weeks after surgery. This survey will be completed by the participants themselves before specimen collection.

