### **Survey**

An ocular symptom/quality of life survey (DEQ-5 and SPEED questionnaires) will be given to the patient to be filled at 1-Day post-op, 1-Week post-op, and 4-Week post-op.

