#### **10.6.3 Adverse Events Data**

We will keep records and report all potential adverse events to the DSMC. Reporting of non-serious and serious adverse events will follow UCSF IRB procedures.

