### **13.4 Timing and Purpose of the DSMC Meetings**

#### **Organizational Meeting**

The initial meeting of the DSMC will be an Organizational Meeting. This is during the final stages of protocol development and the purpose is to provide advisory review of scientific and ethical issues relating to study design to discuss the standard operating procedures and to discuss the format and content of the Open and Closed Reports that will be used to present trial results.

The Organizational Meeting will be attended by all DSMC members, lead trial investigators, and the trial biostatistician. The DSMC will be given the drafts of the trial protocol, the Statistical Analysis Plan, the DSMC Charter, and the current version of the case report forms. At subsequent meetings, committee members will receive Open and Closed Data Reports.

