#### **Open and Closed Reports**

For each DSMC meeting, Open and Closed Reports will be provided. Open Reports will include data on recruitment and baseline characteristics, pooled data on eligibility violations, and completeness of follow-up and compliance. The study statistician ([name]) will prepare these Open Reports.

Closed reports, available only to those attending the Closed Sessions of the meeting, will include analyses of primary and secondary efficacy endpoints, including subgroup and adjusted analyses, AEs and symptom severity, and Open Report analyses that are displayed by intervention group. These Closed Reports will be prepared by the study biostatistician.

The Open and Closed Reports should provide information that is accurate, with follow-up that is complete to within two months of the date of the DSMC meeting. The Reports should be provided to DSMC members approximately three days prior to the date of the meeting.

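### Section 10.6.2 relies on the DEQ-5 and SPEED to identify any adverse event, but both forms ask only about eye symptoms and lubricant use, so other events depend on passive reporting in the text supplied

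*Protocol*

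**What the plan says.** Section 10.6 says that active and passive monitoring are both in place and sets the timing: "We will monitor adverse events at 1-Day post-op, 1-Week post-op, and 4-Week post-op".

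- **Active (10.6.2).** "To identify any adverse events during the study, the research team will administer the survey (DEQ-5 and SPEED questionnaires) to each participant", at those three visits. Participants complete the forms themselves before specimens are taken. No other active method is described.
- **Passive (10.6.1).** The system works "by instructing patients to report any adverse events during the study period". Section 10.5 adds that common reactions are explained at consent and that participants are advised to tell study staff about adverse events at once.
- **Expected events (10.5).** Diarrhea, nausea, dizziness and headache are listed as most common, "each of which may occur as likely as 4% when taking orally and 8% when taking intravenously". Dysphagia and stomatitis are listed as rarer, and diarrhea from *Clostridium difficile* as reported in rare cases.
- **Use of the data.** Section 10.6.3: "We will keep records and report all potential adverse events to the DSMC". In Section 13.5 the Closed Reports are to contain "AEs and symptom severity, and Open Report analyses that are displayed by intervention group", and the DSMC is to see comparative safety results by treatment arm.

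Chapter 5 describes the same instruments more narrowly: "An ocular symptom/quality of life survey (DEQ-5 and SPEED questionnaires) will be given to the patient to be filled at 1-Day post-op", and again at 1 and 4 weeks. The combined document makes the same commitments and reproduces the same questionnaire items.

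**The concern.** The aim stated in 10.6.2 is wider than the tool. Two eye-symptom questionnaires cannot detect an event that they do not ask about and give no space to write down. The protocol itself names the reactions it expects from the study drug, and all of them fall outside both forms.

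The stake is the safety comparison, not the primary endpoint. Eye symptoms are collected by the same questions at the same times in all arms. Everything else, including ocular complications that are not dryness-type symptoms, depends on someone raising it. Participants can tell whether they are using drops: Group 1 has none, and Section 10.1 says that subjects buy the moxifloxacin. Willingness to volunteer a complaint may therefore differ by arm. A DSMC reading a row of zeros could not tell absence of events from absence of questions.

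**Working it through.** This is mainly a comparison of texts. The plan gives no figure of its own to reproduce.

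**1. Answer fields on the two forms (Appendices 3 and 4).**
- DEQ-5: items 1a, 1b, 2a, 2b and 3 = 5 fields.
- SPEED item 1: 4 symptom rows × 3 time windows = 12. Item 2 (frequency) = 4. Item 3 (severity) = 4. Item 4 (lubricant use) = 1. Subtotal 12 + 4 + 4 + 1 = 21.
- Total: 5 + 21 = 26.

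**2. What those fields cover.** DEQ-5 covers eye discomfort, eye dryness and watering. SPEED covers dryness, grittiness or scratchiness; soreness or irritation; burning or watering; eye fatigue; and lubricating drops.

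**3. Events named in 10.5, matched to the forms.**

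| Event | DEQ-5 | SPEED |
|---|---|---|
| Diarrhea | no | no |
| Nausea | no | no |
| Dizziness | no | no |
| Headache | no | no |
| Dysphagia | no | no |
| Stomatitis | no | no |

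Result: 0 of 6. Diarrhea from *C. difficile* is treated here as a form of diarrhea; counted separately, the result is 0 of 7. Nosebleed, which Section 11.3.1 gives as an example of an adverse effect of swabbing, is on neither form.

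**4. Open fields.** The write-in spaces are score totals, the SPEED identification header, and how often lubricating drops are used. Open adverse-event fields: 0.

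**5. Other active routes.** The introduction to Chapter 10 refers the reader to Table 1 for the monitoring schedule. Table 1 has four rows: consent, randomization, specimen collection and survey. None is for adverse events. Section 10.6 gives visit times but describes no staff interview or adverse-event form.

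**6. Illustration only.** With 36 per arm (Chapter 3), a count of zero gives a one-sided 95% upper limit on the event rate of 1 − 0.05^(1/36) = 0.080, or 8.0%, if every event is recorded. If only half were recorded, the limit on the true rate would double to 0.0798 / 0.5 = 0.160, or 16%. The one-half is my assumption. The documents contain nothing from which to estimate capture, so this shows the direction of the problem and does not measure it.

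**The case against.** **Other routes exist.** Passive reporting is stronger than a bare instruction: reactions are explained at consent and participants are told to report events immediately. This stands, and it rules out an inference that the trial has no means of capturing non-ocular events. It remains passive, whereas 10.6 claims an active system as well.

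**The forms may exist elsewhere.** Section 13.4 says the DSMC receives "the current version of the case report forms", data go into REDCap, and adverse-event reporting follows UCSF IRB procedures. Neither the case report forms nor the SAP text was available to me. A reader might infer that structured adverse-event collection is absent from the trial. The documents do not show that. They show that 10.6.2 and Table 1 neither describe nor cite any.

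**The expected rates may not apply.** The 4% and 8% in 10.5 are for oral and intravenous use, and no rate is given for intracameral or topical use. This also stands. The mismatch in step 3 does not depend on any rate, but no number of missed events can be derived.

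**No pre-operative survey.** It is tempting to add that, without a baseline survey, neither form can show that an eye symptom is new. That is wrong. On a 30-day month, the past-month window of the day-1 DEQ-5 is 29/30 = 97% pre-operative, and at 4 weeks it is 28/30 = 93% post-operative, so a rise between them is evidence of change. SPEED item 1 also has a three-month column that can be compared with current symptoms at later visits. Both rest on recall, but they are informative. Nor does any passage say that adverse-event tables will use the SPEED total, so a claim that symptom timing is lost through the scoring has no support.

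**Rewording alone would suffice.** The relevant subsection is headed as an ocular symptom survey, so narrowing its stated aim would remove the contradiction. True, but that would leave the plan with no described active method for any other event.

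**Conclusion.** The point holds as a gap in active ascertainment. The only active tool described for any adverse event covers 0 of the 6 events named in 10.5 and has no open field. In the supplied text, non-ocular events and other ocular complications reach the DSMC only by passive report or staff observation, so a low or zero count in those rows is hard to interpret.

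It should be corrected, but it is not critical: the primary resistance endpoint is untouched, passive capture exists, and Section 11.3.2 describes all the regimens as common in current practice. Confidence is moderate, because the conclusion assumes that no adverse-event form sits in the unseen case report forms or SAP. If one does, the defect shrinks to a missing cross-reference. The number of events that would be missed cannot be stated.

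**What to change.** In 10.6.2 and Table 1, add a brief uniform adverse-event query at the existing 1-day, 1-week and 4-week visits, or cite the case report form if it already contains one. The query should:

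- ask about the period since surgery or since the last visit;
- cover the events named in 10.5 and include one open question, which also allows other ocular complications to be recorded;
- record onset date and seriousness;
- be tabulated by arm for the DSMC.

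Describe the DEQ-5 and SPEED as ocular symptom measures and drop the claim that they identify any adverse event.

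**Cost.** One protocol amendment with IRB review, one REDCap form, and 108 × 3 = 324 short forms at visits that already take place. Staff time, on my assumptions:

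- entry and review at 2 to 5 minutes each: 324 × 2/60 = 10.8 h to 324 × 5/60 = 27.0 h;
- follow-up of positive answers (5% to 20% of forms, 10 to 15 minutes each): 16.2 × 10/60 = 2.7 h to 64.8 × 15/60 = 16.2 h;
- building the form: 2 to 4 h;
- total: about 16 to 47 h, excluding the amendment.

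The main drawback is noise. Prompting will add non-specific complaints, about 16 to 65 records on these assumptions, and 10.6.3 sends them to the DSMC. The query also does not remove reporting bias from participants who know whether they have drops, and 36 per arm cannot exclude rare events. Both limits should be stated. If a suitable form already exists, the cost is one cross-reference.
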